8.2.1. Inclusion criteria

This study can only achieve its aims if the appropriate patients are included. The following inclusion and non-inclusion criteria are designed to select patients for whom the protocol is deemed appropriate by their physician.

- Man or woman aged 18 or over;
- Patient suffering from a/mRCC, receiving sunitinib first-line treatment, as per SPC recommendations;
- Resolution (grade ≤ 1 according to CTCAE version 4.03 of June 2010) of all acute toxic effects due to radiotherapy or surgical procedure prior to initiation of sunitinib;
- Patient who can be monitored for 6 months.
- Female patient of child-bearing age using a form of contraception during treatment with Sunitinib and for at least 28 days after termination of treatment with Sunitinib;
- Patient having signed his/her consent form;
- Patient affiliated with a social security scheme.

8.2.2. Non-inclusion criteria

- Patient participating in a clinical trial during sunitinib treatment;
- Patient managed by a home hospitalisation service during sunitinib treatment;
- Patient taking part in therapeutic education programmes, or benefiting from nursing consultation, or from any other significant treatment support and likely to impact adverse event management.
- Patient untreated and/or symptomatic brain metastases prior to sunitinib initiation;
- Patient refusing the use of his/her personal data.
- Patient with an ECOG performance status upon inclusion > 2 ;
- Patient presenting with a serum creatinine level > 1.5 times the upper limit of the normal level;
- Patient presenting with a bilirubin level > 2 mg/dl, aspartate transaminase (ASAT) or alanine transaminase (ALAT) > 2.5 times the upper limit of the normal value, or > 5 times the upper limit of the normal value in the presence of liver metastases upon initiation of sunitinib treatment.
- Patients who are staff members of a centre involved in the study, or close to one of the staff members of a centre directly involved in conducting the study, or patients employed by Pfizer and involved in conducting the study

8.3. Variables

8.3.1. Table of recorded data

During the routine patient consultations at the centres:

	V1: Inclusion T0	V2: end of cycle 1 W6	V3: end of cycle 2 W12	V4: end of cycle 4 W24
Data filled in by the physician via the e-CRF				
Compliance with eligibility criteria	x			
ECOG performance status	x	x	x	x
Sociodemographic characteristics	x			
History of the disease	x			
Disease progression		x	x	x
Biological, histological and metastatic examination data	x	x	x	x
Conditions of sunitinib use	x			
Modification of conditions of sunitinib use		x	x	x
Concomitant treatments	x	x	x	x
Pharmacovigilance data		x	x	x
Medical procedures (calls, consultations, hospitalisations), planned or unforeseen		x	x	x
Issuing of Sunitinib treatment support equipment	x	x	x	x
Data filled in by the patient (self-questionnaire)				
Compliance (Morisky)		x	x	x
Data filled in by the physician and the patient				
Satisfaction concerning the call centre filled in by the physician and the patient				x

8.4. Data sources

8.4.1. Data recorded by the physician:

Upon inclusion

The inclusion visit enables the physicians to document the following parameters:

- Compliance with inclusion criteria;
- ECOG performance status;
- Patient's sociodemographic characteristics;
- History of the disease;
- Biological, histological and metastatic examination data;
- Conditions of sunitinib use;
- Concomitant treatments;
- Issuing of treatment support equipment and planned support.

During the end-of-cycle 1, 2 and 4 visits

During the follow-up visits, the following parameters are recorded by the physicians, via the e-CRF:

- Disease progression;
- Biological, histological and metastatic examination data;
- Possible modifications to the conditions of sunitinib use (change of dose, treatment plan, temporary interruption or termination);
- Concomitant treatments;
- Pharmacovigilance data (recording of adverse events, degree of severity and description of the AE: intensity, symptoms, impact on patient follow-up, examinations performed, actions implemented);
- History of calls and consultations with a healthcare professional during the cycle (scheduled and unscheduled).
- Hospitalisation during the cycle (scheduled and unscheduled).
- Issuing of treatment support equipment and planned support.

The end of cycle 4 visit will represent the final visit.

At the end of the study

The participating physicians will fill in on the e-CRF a questionnaire on their level of satisfaction concerning the call platform.

8.4.2. Data recorded via the call centre:

The patients will have received phone calls on W1, W2, W3, W4 and W5 of the first two cycles, then every two weeks, W2 and W4 for cycles 3 and 4.

During the calls made by the nurses, all of the data of the specific call questionnaires (Appendix 6: Nurse intervention script) shall be recorded via a CATI system used to instantaneously enter the data collected into a software application.

The following data will be collected:

- Number of call attempts
- Patient's general condition;
- Treatment taking;
- Tolerance and occurrence of adverse events (description of the AE: intensity, symptoms, impact on the patient, examinations performed, actions implemented;
- Proposed action

A summary of calls shall be issued to the participating physicians. The adverse events collected during the calls shall be recorded in the participating physicians' CRF with a view to validating them during the follow-up visits performed by the participating physician.

8.4.3. Data recorded by the patient:

The patients shall be asked to fill in 2 self-questionnaires:

- The Morisky questionnaire (Appendix 10): 4 items used to evaluate treatment compliance with one additional item concerning the occurrence of adverse events. This questionnaire shall be filled in at the end of the 6th week of cycles 1, 2 and 4;
- A satisfaction questionnaire (Appendix 11) concerning the call platform (drawn up in the context of this study) filled in during the end-of-study visit (6th week of cycle 4), or upon treatment termination.

8.5. Complete population justification (physicians/patients)

The patients included in this study will receive support from a therapy management platform in addition to usual follow-up by their oncologist.

The estimated number of patients (n) is determined by the precision (i) required when estimating the proportion (p) of patients presenting with at least one grade 3 or 4 AE. A 95% confidence interval is associated with the estimation of this proportion. The smaller the amplitude of this confidence interval, the greater the precision. Precision is given by the following formula:

$$i = 1.96 \sqrt{\frac{p(1-p)}{n}}$$

Depending on the observed proportion and on the size of the studied population, the following precision levels may be achieved:

Observed proportion	Resulting precision		
	n=75	n=100	n=125
10 – 90	6.8	5.9	5.3
20 – 80	9.1	7.8	7.0
30 – 70	10.4	9.0	8.0
40 – 60	11.1	9.6	8.6
50	11.3	9.8	8.8

Precision is minimum where the amplitude of the maximum confidence interval for a given proportion is equal to 50%. Failing any hypothesis concerning the value of the expected proportion, the hypothesis of a 50% proportion will be used. Thus, we can show that 100 patients will need to be included to estimate a percentage with a 95% confidence interval whose amplitude does not exclude $\pm 9.8\%$.

Between 10 and 20 centres are expected to participate in France, that shall each include 10 patients on average.

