7.3 Evaluation criteria

7.3.1. Main outcome measure

The main outcome measure is defined by the proportion of patients presenting with at least one grade 3 or 4 adverse event (whether associated to Sutent® or not) during the first 4 treatment cycles (study follow-up period), based on the 'Common Terminology Criteria for Adverse Events' (CTCAE) version 4.03 of June 2010.

Adverse events shall be collected:

- via the e-CRF, by the physicians, during routine follow-up consultations,
- Via the CATI system, by the call centre nurses during phone calls. Declaration to the Pfizer Pharmacovigilance department within the statutory time limits by the CATI system at the end of each patient interview. AEs will also be sent to the participating physicians via the e-CRF for review and validation during the patient follow-up visits.

Adverse events precisely described to the nurses by the patients, with a proposed gradation by the nurse where applicable, shall be definitively graded by the participating physician during the patient consultations at the centre, according to the CTCAE version 4.03 of June 2010, available from the study website.

Pharmacovigilance files (AE report form and additional file generated from the CRF data) shall automatically be created from the e-CRF. One file shall be created for each AE upon completion of the visits made by the participating physician and after approval of all reported cases.

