The therapy management platform will be managed via a call centre using a CATI (Computer-Assisted Telephone Interview) system. This system is used to instantly enter into the computer all the data collected in response to specific questionnaires submitted by the nurses during the telephone calls, in the context of follow-up.

Patient management varies widely according to the physician and his/her patients' needs. To avoid interfering in follow-up practices, each physician shall follow up their own patients according to their usual practices.

Population of participating physicians

The study shall be proposed to 58 physicians at 50 oncology centres in metropolitan France caring for patients suffering from metastatic/advanced renal cell carcinoma.

Each physician shall be questioned concerning the annual number of patients meeting the inclusion and non-inclusion criteria. It shall also be questioned concerning the systems in place in their centre.

Thus, each centre receiving at least 10 patients per year and that does not already possess a coordinating nurse or platform for routine patient follow-up may be selected to take part in this project, forming the list of identified physicians.

This step, conducted upstream of the study, will allow the identification of 20 to 25 physicians eligible to take part in the study.

A description of the sample of centres shall be provided subsequently, based on the identification data of the participating physicians from each centre (age, gender, geographical situation, etc.). We shall then check that the sample of participating physicians is representative of oncologists in France in terms of centre size and type, in order to guarantee external study validity.

The patients included in the RENACALL study will be monitored not only in the standard manner, but also via the therapy management platform. In the context of standard follow-up, they will be issued the usual logbooks for their treatment, along with any documents routinely used by the centres.

Patient follow-up via a therapy management platform consists in making regular phone calls (14 during the first 4 cycles) to support the patients in the management of their sunitinib treatment.

The calls shall be made from a centralised therapy management platform located in the Paris region, by nurses specifically trained for this role. If necessary, the nurses may be assisted by physicians from the platform.

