8.7.3. Analysis plan

Main outcome measure analysis

The proportion of patients presenting with at least one grade 3 or 4 AE (whether associated with sunitinib or not) shall be estimated in the overall population of patients treated with sunitinib. A 95% confidence interval will be associated with the observed proportion, using the asymptotic method, or the Clopper-Pearson exact method.

Analysis of secondary outcome measures

The analysis of secondary objectives shall be detailed in the statistical analysis plan.

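### The ±9.8% precision and the planned interval assume independent patients, although 100 patients come from 10–20 centres; if outcomes correlate within centres, the interval may be too narrow

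*Protocol*

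**What the plan says.** Protocol 8.5 bases the sample size on precision alone, with i = 1.96√(p(1−p)/n). Having no expected value for the proportion, it says that "the hypothesis of a 50% proportion will be used" and concludes that "100 patients will need to be included to estimate a percentage with a 95% confidence interval" of ±9.8%. On where the patients come from it says: "Between 10 and 20 centres are expected to participate in France, that shall each include 10 patients on average".

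For the primary result, Protocol 8.7.3 plans: "A 95% confidence interval will be associated with the observed proportion, using the asymptotic method, or the Clopper-Pearson exact method". SAP 8.2.4 says only that the proportion will be estimated. The shell of SAP Table 30 leaves room for an interval but names no method. SAP 8.1.1 describes the whole analysis as descriptive.

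On the endpoint, Protocol 7.3.1 says that events reported to the nurses "shall be definitively graded by the participating physician during the patient consultations at the centre", using CTCAE v4.03. Protocol 8.2 says that "Patient management varies widely according to the physician". The same sentence goes on to name the patients' needs as a second source of variation, and the text then leaves each physician to follow usual practice.

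No ICC, design effect, centre-stratified estimate or cluster-robust interval appears in either document.

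**The concern.** The sample-size formula and both intervals named in Protocol 8.7.3 are valid for independent patients. Patients at one centre share a physician or a small team, local habits of prevention and supportive prescribing, and the person who sets the final grade. Each of these could make outcomes within a centre more alike than outcomes across centres. The variance of the overall proportion would then exceed p(1−p)/n, and a nominal 95% interval would cover less often than stated.

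This matters because the study has no hypothesis test (SAP 4.1), so the primary finding is an estimate and its stated uncertainty. SAP 3 also allows the results to be discussed against the French real-life cohort for which Protocol 6.1.2 gives 58%. As a hypothetical case, an observed 47% has a simple asymptotic interval of 47 ± 9.8, or 37.2–56.8, which excludes 58%. With 10 patients per centre and an assumed ICC of 0.05 the half-width is 9.78 × √1.45 = 11.8, and the interval of 35.2–58.8 includes it.

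**Working it through.** **Inputs.** From Protocol 8.5: n = 100, p = 0.50, z = 1.96, 10–20 centres. A mean of 10 patients in 10–20 centres would give 100–200 patients, so with 100 patients the mean per centre is m = 10 (10 centres) or m = 5 (20 centres). The ICC is **not in the documents**. It is assumed, and shown from 0.01 to 0.10.

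**Step 1: the plan's own figure.** 1.96 × √(0.5 × 0.5/100) = 0.098, or 9.8 points. This reproduces, as do all 15 cells of the precision table. The arithmetic in 8.5 is correct under independence.

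**Step 2: half-width with clustering.** Design effect DE = 1 + (m − 1) × ICC; half-width = 9.8 × √DE; effective n = 100/DE.

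**Step 3: coverage of the simple intervals.** For the asymptotic interval, the normal approximation is 2Φ(1.96/√DE) − 1. For Clopper-Pearson, coverage was computed by summing independent beta-binomial centres (a further assumption) at p = 0.5, and counting the totals whose interval contains 0.5. At 50/100 the Clopper-Pearson interval is 39.8–60.2, a half-width of 10.2.

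| m | ICC | DE | Effective n | Half-width (points) | Asymptotic coverage | Clopper-Pearson coverage |
|---|---|---|---|---|---|---|
| 5 | 0.01 | 1.04 | 96 | 10.0 | 94.5% | 96.1% |
| 5 | 0.02 | 1.08 | 93 | 10.2 | 94.1% | 95.7% |
| 5 | 0.05 | 1.20 | 83 | 10.7 | 92.6% | 94.5% |
| 5 | 0.10 | 1.40 | 71 | 11.6 | 90.2% | 92.4% |
| 10 | 0.01 | 1.09 | 92 | 10.2 | 94.0% | 95.6% |
| 10 | 0.02 | 1.18 | 85 | 10.6 | 92.9% | 94.7% |
| 10 | 0.05 | 1.45 | 69 | 11.8 | 89.6% | 91.9% |
| 10 | 0.10 | 1.90 | 53 | 13.5 | 84.5% | 87.2% |

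The two coverage columns use different methods. Under the same beta-binomial calculation the asymptotic figures are 0.7 to 1.4 points lower than shown, so Clopper-Pearson's advantage does not come from the choice of method.

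**Step 4: two checks.**
- *Does planning at p = 0.50 absorb the effect?* At p = 0.58 the independent half-width is 1.96 × √(0.58 × 0.42/100) = 9.7 points, a gain of only 0.1.
- *Do unequal centre sizes matter?* With an assumed coefficient of variation of 0.6, DE = 1 + (1.36m − 1) × ICC. At m = 10 and ICC 0.05, DE = 1.63 and the half-width is 12.5 instead of 11.8.

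**The case against.** Several objections carry weight.

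- **The whole effect is assumed.** No ICC is given. At ICC 0.01 the loss is 0.2–0.4 points, and Clopper-Pearson, one of the two planned methods, still covers at least 95%. This stands, and it limits the point to a possibility.
- **The sentence on variable management does not show variable grading.** A reader might infer from it that physicians grade differently, and so that the interval is probably or certainly too narrow. The documents do not support that. The sentence concerns management and also cites patients' needs. Grading follows CTCAE v4.03, and nurses on one central platform propose grades from a scripted table with numeric cut-offs (Protocol Appendix 7). These features should dampen centre effects. They do not remove them, because the local physician sets the final grade and the preventive and supportive prescriptions remain local.
- **Ten per cluster is the extreme case.** Protocol 8.2 expects 20 to 25 physicians, so 100 patients give 4–5 per physician. At that size, ICC 0.02–0.10 gives about 10.1–11.6 points. This stands, and is why both ends of the range are shown. Ten centres of ten nevertheless lies within what 8.5 plans.
- **No decision depends on the interval.** This is true, and it keeps the point minor. The interval is still the only statement of uncertainty attached to the primary proportion.
- **A clustered interval from 10–20 centres is itself unstable.** This is also true. It is a reason to report it beside the simple interval and not in its place. The listing of GEE among the SAP abbreviations is not evidence of intent, since the SAP text never uses it.

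**Conclusion.** The point holds as a possibility worth a sensitivity analysis. The ±9.8% is correct only if outcomes are uncorrelated within centres, and neither document states that condition. For assumed ICCs of 0.02–0.10 the half-width is 10.2–11.6 points with 20 centres of 5 and 10.6–13.5 with 10 centres of 10. Under-coverage is material mainly at ICC 0.05–0.10 with about 10 patients per centre, and small at ICC 0.01–0.02.

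Two stronger readings should be resisted. A reader might take coverage near 84% as the expected performance of the planned analysis. It applies only to the asymptotic interval, at the top of the assumed ICC range and with the fewest centres. A reader might also conclude that the sample size is inadequate. The documents set no precision threshold that a half-width of 11 or 12 points would breach, so the figures support restating the precision and not enlarging the study. The results rest on the assumed ICCs, near-equal centre sizes and, for the Clopper-Pearson coverage, a beta-binomial model at p = 0.5.

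**What to change.** In Protocol 8.5, state that ±9.8% assumes no within-centre correlation, and that over 5–10 patients per centre and an assumed ICC of 0.02–0.10 the half-width would be about 10.2–13.5 points.

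In SAP 8.2.4, name which simple interval from Protocol 8.7.3 is to be used. Add as a sensitivity analysis a centre-clustered interval for the same proportion, for example from an intercept-only logistic GEE with exchangeable correlation and a small-sample-corrected robust variance. Report the estimated ICC with it, and add a row to Table 30.

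The cost is a few lines of SAS, already the specified software; the centre number is already part of the patient code (Protocol 9.1). The drawbacks are a less favourable stated precision, and an ICC and robust variance that will be imprecise with only 10–20 centres. Similar simple and clustered intervals would give some support to the stated precision; clearly different ones would show the reader how far it depends on independence.

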8.6. Data management

The CRO in charge of data management will process the RENACALL study data for all patients. These data will be in electronic form for data collected from the physician during the visits, along with data entered into the CATI system during calls, and in hard copy form for data collected from the patients.

All data management operations will be performed in accordance with Pfizer requirements and with CRO Standard Operating Procedures.

A data management plan, used to define and describe all biometrics activities, shall be developed by the CRO and submitted to Pfizer for validation.

8.6.1. Database construction

An annotated questionnaire shall be prepared by the CRO in charge of data management. This document will list the names of the tables and variables. For each variable, the document will give its type, length and format if applicable. The annotated questionnaire will be submitted to Pfizer for validation.

The CRO will then create a database using its own software. The structure of the database will be documented and checked on printouts, comparing the attributes of the database variables to the specifications listed on the annotated questionnaire.

Before actual data entry, the database structure and input screens will be tested and validated in accordance with the CRO and Pfizer Standard Operating Procedures. For this purpose, a number of fictitious questionnaires, generally between 3 and 5, will be filled in and entered. Validation will be performed by printing out the data and comparing them to the data on the questionnaires. A validation report shall be drafted and submitted to Pfizer. The final database structure shall be submitted to Pfizer for validation before any actual data can be entered.

An audit file shall be created to save any changes made to the database. The original datum, the modified datum, the modification date and time, along with the person who made the change and the reason for the change shall be recorded in the audit file. Audit file function will be tested by altering fictitious data. A report shall be drafted and submitted to Pfizer.

8.6.2. Data input

Once the database has been validated by Pfizer, the hard copy questionnaires will be entered in duplicate using the CRO's software. Periodic input progress reports will be printed by the CRO and sent to Pfizer.

8.6.3. Data control

A list of consistency checks used to detect any inconsistencies or aberrant answers in the questionnaires shall be printed by the CRO and validated by Pfizer. These checks will be programmed using the CRO's software, then tested on fictitious data. These fictitious data, along with test-related documents, shall be kept in the study binder by the CRO and made available for review by Pfizer.

After input, the checks shall be performed continuously: a query specific to each inconsistency shall be generated electronically by the data control system. In order to limit the number of queries submitted to the participating physicians, a guide to obvious corrections can be prepared by the CRO and validated by Pfizer.

The CRO shall provide the data control documents on simple request by Pfizer. Periodic control progress reports will be printed by the CRO and sent to Pfizer.

8.6.4. Coding

All reported adverse events shall be entered using the MedDRA coding dictionary.

For other codings, a computer program shall be used to assign a code and preferred term to the verbatim text. The dictionary used shall be defined in collaboration with Pfizer.

